5.2 Schedule of Events for AMKL Patients

	Baseline	On-Treatment ⁱ						Off-Treatment		
	Screening	Cycle 1 ^a				Cycles 2-6 ^p +/- 2 days		Cycle 7+ ⁱ +/- 2 days	EOT Visit ⁿ	EOS Visit ^o
		D1 ⁱ	D4 (+/-1d)	D8 (+/-2 d)	D15 (+/-2 d)	D1 ⁱ	D15			
Informed consent ^v	X									
Medical history ^q	X									
Physical exam ^b	X	X		X	X	X		X	X	X
ECOG status ^r	X	X		X	X	X		X	X	X
Vital signs ^c	X	X		X	X	X		X	X	X
12-lead ECG ^d	X									
Hematology ^{e,s}	X	X	X	X	X	X	X	X	X	X
Chemistry ^{f,s}	X	X	X	X	X	X	X	X	X	X
DIC screen ^{g,s}	X									
PT(INR)/aPTT ^g		X	X	X	X	X				
Pregnancy test ^{h,s}	X	X								
Bone marrow biopsy & aspirate ^k	X					X		X	X	
Bone marrow collection for PD studies ^{i,j}						X				
Blood collection for PD studies ^{i,j}		X			X	X	X			
Buccal swab (Optional) ^u	X									
Treatment ^m					X					
Adverse events ^t	X	X		X	X	X		X	X	X
Concomitant meds	X	X		X	X	X		X	X	

^a One cycle = 21 days

^b Includes height (baseline only) and weight. Baseline physical Exam within 14 days of registration.

^c Vital signs include diastolic and systolic blood pressure, heart rate, and oral temperature; C1D1 vital signs should be taken pre-dose(+/-30 mins) as well as about 2 hours(+/-30mins) post dose.

^d A 12-lead ECG will be performed at baseline and thereafter only as clinically indicated. Baseline ECG within 14 days of registration

^e Hematology panel to include hematocrit, hemoglobin, white blood cell count with differential, and platelet count. Samples should be collected days 1, 4, 8, and 15 of cycle 1, days 1 and 15 of cycles 2-6, and then day 1 of all cycles thereafter (a window of +/- 2 days is permitted for all timepoints). See footnote s.

^f Chemistry panel to include the following: BUN, creatinine, sodium, potassium, chloride, bicarbonate, glucose, uric acid, LDH, total bilirubin, direct bilirubin, ALP, AST (SGOT), ALT (SGPT), albumin, magnesium, phosphate, and calcium. Samples should be collected days 1, 4, 8, and 15 of cycle1, days 1 and 15 of cycles 2-6, and then day 1 of all cycles thereafter (a window of +/- 2 days is permitted for all timepoints). See footnote s.

- ^g Disseminated intravascular coagulation (DIC) screen should include: PT/INR, aPTT, fibrinogen, and D-dimer. Cycle 1 day 1 PT/INR/aPTT does not need to be performed if the screening DIC was within 3 days of this visit. If the initial DIC is positive follow-up coagulation studies should include the full DIC panel (rather than the PT/INR/aPTT alone). See footnote s.
- ^h Serum pregnancy test required for women of child-bearing potential during screening AND pre-dose on Cycle 1 day 1. Results must be available and negative prior to dosing. See footnote s.
- ⁱ It is strongly preferred that correlative samples be collected and shipped only on Monday – Thursday (with same day shipment preferred). Friday collections/shipments should be avoided to ensure sample stability. Since these samples are collected on Day 1 of each cycle, it is preferred that Day 1 visits be conducted on Monday through Thursday when correlative samples are being collected. Sites should use the available windows to achieve this. Please contact the QAM if there are any questions.
- ^j Peripheral blood (25 ml) and/or bone marrow (if done will collect about 10-20 ml) samples will be collected for determination of alisertib pharmacodynamics (PD studies). Samples will be collected at the start of each cycle(D1). Sample collection at D15 will be optional. Samples will be collected for a maximum of 6 cycles. Please refer to laboratory manual for details.
- ^k Bone marrow aspirate and biopsy will be performed at screening (within 21 days prior to registration), cycle 2 day 1, and after cycle 4 (between days 21 and 35). For patients not yet in CR after cycle 4, bone marrow aspirate and biopsy should be repeated after cycle 6 (between days 21 and 35). Thereafter bone marrows should be repeated as clinically indicated.
- ^l Labs and exam only required on day 1 of cycles 7 and beyond (although additional may be performed as clinically indicated).
- ^m Patients will be administered orally on days 1-7 of each cycle (1 cycle = 21 days); patients may remain on treatment until development of unacceptable toxicity or progression of disease.
- ⁿ Patients will have an end of treatment (EOT) visit approximately 30 days (+10 days) after the last dose of treatment; if a bone marrow was carried out at disease progression, this will be considered the EOT marrow and does not need to be repeated at the EOT visit.
- ^o Patients will have a final end of study (EOS) visit approximately 6 months (+/- 30 days) after the last dose of treatment to assess for late-onset toxicity.
- ^p Labs *required* only on days 1 and 15 of cycles 2-6, but in the event of cycle 1 toxicity or at treating investigator's discretion, additional interim labs may be performed per standard of care.
- ^q Baseline Medical History within 14 days of registration
- ^r Baseline ECOG Status within 14 days of registration.
- ^s Baseline Hematology, Chemistry, DIC screen, Pregnancy Test, within 7 days of registration
- ^t Baseline Adverse Events and Concomitant Medications within 14 days of registration.
- ^u For subjects signing optional consent.
- ^v Informed consent should be obtained within 28 days of registration.

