2.3 Exploratory Objectives & Endpoints

Exploratory objectives will include the following:

- 2.3.1 Describe pharmacodynamics (PD) effects of alisertib in peripheral blood and/or bone marrow samples.

Serial blood and/or bone marrow samples will be collected at specific timepoints. Flow cytometry, colony forming assays, AURKA autophosphorylation assays, and in vitro cultures of patient specimens to assess the effect of MLN8237 on megakaryocytes and other hematopoietic cells will be measured.

- 2.3.2 Evaluate the relationship between biomarker expression levels and response to alisertib.

Changes in biomarker expression levels from baseline will be measured (using PD samples) to correlate with response to alisertib therapy. Biomarkers will include a) genes encoding key enzymes in Aurora kinase signaling, b) markers of cellular aneuploidy and apoptosis, and c) markers of megakaryocytic differentiation.

- 2.3.3 Evaluate reduction in splenomegaly by palpation (MF arm only).

Patients will be examined for splenomegaly by palpation once per cycle and change from baseline will be calculated over time.

- 2.3.4 Evaluate improvement in MF symptoms (MF arm only), as assessed by the Myeloproliferative Neoplasm Symptom Assessment form (MPN-SAF).

The MPN-SAF will be administered to patients in the MF arm only once per cycle. Changes in symptom scores over time will be calculated.

- 2.3.5 Assess change in bone marrow fibrosis in patients in the MF arm. Bone marrow will be assessed at screening and after cycle 6 in this population.

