9.0 CORRELATIVE STUDIES

9.1 Sample Collection

Blood and/or bone marrow samples for PD studies will be collected at multiple timepoints for cycles 1-6. Samples will be collected at the time of routine blood and/or bone marrow collection on Day 1 of each cycle. Sample collection on Day 15 will be optional. For MF patients, only peripheral blood samples will be collected unless bone marrow is deemed medically necessary; AMKL patients may include both blood and bone marrow procurement. Approximately 25 ml of peripheral blood and 10-20 ml of bone marrow will be collected in lavender top EDTA tubes and dark green top tubes respectively, and labeled with the patient initials, study number, and date of collection. Samples may sit at room temperature until they are picked up or shipped.,.

As mentioned above, correlative bone marrow samples should be obtained any time bone marrows are collected as clinically indicated during study participation. At baseline, bone marrow collection is not required for study entry, but study team should request 3-4 unstained slides from prior bone marrow testing performed within the last year. Unstained slides should be shipped at room temperature to [name]

It is strongly preferred that correlative samples be collected and shipped only on Monday – Thursday (with same day shipment preferred). Friday collections/shipments should be avoided to ensure sample stability. Since these samples are collected on Day 1 of each cycle, it is preferred that Day 1 visits be conducted on Monday through Thursday when correlative samples are being collected. Sites should use the available windows to achieve this. Please contact the QAM if there are any questions.

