9.3 Processing and Analysis

Upon receipt, monocuclear cells will be collected from the samples by Ficoll preparation. Aliquots of the cells will be used in the following ways:

1. To extract RNA for gene expression studies. We will determine the pathways that are up or down-regulated upon Alisertib treatment. We anticipate changes in cell cycle regulatory and megakaryocyte differentiation pathways.

2. To isolate proteins for analysis of levels of key factors, such as transcription factors, ribosome assembly proteins, and signaling molecules. We will use western blot assays to determine the changes that occur with Alisertib treatment.
3. To perform flow cytometry will be performed to analyze the state of maturation of the cells, including CD41, CD42 expression and DNA content. We will use FlowJo software to analyze the flow cytometry data to determine the levels of these differentiation parameter.
4. To perform flow cytometry to assess the state of signaling cascades, such as the AKT, ERK, and STAT pathways. We will use FlowJo software to analyze the flow cytometry data to determine the levels of activation of these pathways.
5. To perform flow cytometry to assess the hematopoietic stem cell compartment. We will use FlowJo software to determine the different populations of hematopoietic stem and progenitor populations.
6. To culture in vitro and in vivo to assess the state and differentiation potential of hematopoietic progenitor cells.
7. We may elect to use samples at a later time point to directly compare differences in gene expression and signaling pathways from sequential patient specimens. Thus, we will freeze down aliquots of cells, and/or or RNA, and/or protein for future cell culture, flow cytometry, DNA, RNA and protein extractions. Samples will be kept for up to two years.
8. An optional correlative study (separate patient consent) will involve exome or whole genome sequencing on normal and tumor DNA for patients with AMKL. DNA from tumor samples will be available as in line 7 above; to obtain germline DNA, buccal swabs will be obtained.

Samples will be labeled with a number and not the patient names. Identifying information will be retained by the PI and co-investigators and not shared with the laboratory staff. Identities of the subjects will not be reported in presentations or publications.

Samples will be retained indefinitely in [name] laboratory located at Northwestern University.

Please refer to laboratory manual for more details.

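### In AMKL, no fresh pre-treatment marrow sample for the pharmacodynamic studies is scheduled or assured, although a screening marrow is mandatory

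*Combined protocol and SAP*

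**What the plan says.** Section 2.3.2 defines the biomarker endpoint: "Changes in biomarker expression levels from baseline will be measured (using PD samples) to correlate with response to alisertib therapy". PD samples are blood and/or marrow throughout the protocol. Section 10.1.3 relates the changes to response with a Wilcoxon rank sum test.

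For AMKL, Section 5.2 footnote k fixes the marrow dates: "Bone marrow aspirate and biopsy will be performed at screening (within 21 days prior to registration), cycle 2 day 1, and after cycle 4", with a further marrow after cycle 6 for patients not yet in CR. Footnote j sets the PD dates: "Samples will be collected at the start of each cycle(D1", for at most six cycles, and makes marrow conditional: "bone marrow (if done will collect about 10-20 ml". In the AMKL table, the row "Bone marrow collection for PD studies" has no mark under Screening or cycle 1 day 1.

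Section 9.1, in text not limited to MF, says: "At baseline, bone marrow collection is not required for study entry, but study team should request 3-4 unstained slides from prior bone marrow testing". The slides may come from any marrow of the previous year. The sentence before it asks for correlative marrow whenever a marrow is collected as clinically indicated during participation. Section 9.3 describes the laboratory work: "monocuclear cells will be collected from the samples by Ficoll preparation", and then lists RNA, protein, flow cytometry and culture.

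**The concern.** A change from baseline needs a sample taken before the first dose. In AMKL the protocol already performs a pre-treatment marrow on every patient but does not assign any of it to the PD studies. The first marrow that meets the PD sampling rule comes after 7 dosing days and 14 rest days.

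What is at stake is the marrow part of two exploratory aims: describing PD effects in marrow (2.3.1), and relating change in ploidy, apoptosis and megakaryocytic differentiation markers to response (2.3.2). A marrow series that begins at cycle 2 has no untreated reference, and none can be obtained once dosing has started. AMKL patients may be few. The total of 24 is shared with MF, and the history of changes explains the flexible split by the greater availability of MF patients. Each lost pair therefore counts.

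**Working it through.** No formula applies. The check sets the AMKL schedule rows beside footnotes j and k.

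| Time point | Clinical marrow | PD marrow | PD blood |
|---|---|---|---|
| Screening | required | no entry | no entry |
| Cycle 1 day 1 | none | no entry | yes |
| Cycle 2 day 1 | required | yes | yes |
| After cycle 4 | required | only if it counts as a Day 1 sample | yes, on Day 1 |
| After cycle 6 | if not in CR | no entry | no entry |
| End of treatment | yes, unless a progression marrow stands in | no entry | no entry |

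1. **Count.** A patient who completes six cycles has 4 scheduled clinical marrows (screening, cycle 2 day 1, after cycle 4, end of treatment), or 4 + 1 = 5 if not in CR after cycle 4. One of these precedes treatment. Pre-treatment marrows with a PD entry: 0.

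2. **Does the conditional wording in footnote j rescue it?** No. It applies to Day 1 of a cycle, and footnote k puts no marrow on cycle 1 day 1.

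3. **Does the table leave screening items unmarked as a habit?** No. The optional buccal swab, also a correlative item, is marked under Screening in the same table.

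4. **Can the slides stand in?** Not for the assays in Section 9.3, which start from separated mononuclear cells. That section names no slide-based assay. The slides are only to be requested and may be up to a year old. With a washout of only 14 days (Section 3.3.2), they may also predate intervening therapy.

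5. **Can blood stand in?** For blood markers, yes, because a sample is scheduled on cycle 1 day 1. Footnote j does not say that it is taken before the dose, whereas footnotes c and h do say so for vital signs and the pregnancy test. It is not a marrow baseline.

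6. **Could consent precede the screening marrow?** Yes. Consent is allowed up to 28 days before registration and the marrow up to 21 days before, so the consent window opens 28 - 21 = 7 days earlier. Both limits are maxima and neither sets an order.

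**The case against.** A reader might infer that marrow change from baseline cannot be computed in AMKL, or is missing for every such patient. The documents do not support that, for three reasons.

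- The Section 9.1 clause on clinically indicated marrows is not restricted to MF and could be read to cover a screening marrow taken after consent. The reading is arguable. Footnote k distinguishes its scheduled marrows from later ones done as clinically indicated, and the clause is repeated in the MF footnote j but not in the AMKL one. Still, it leaves room for a site to take the sample.
- Waiving baseline marrow as a condition of entry does not forbid it.
- The objectives accept blood or marrow, Section 9.1 treats AMKL marrow procurement as something that may be included, and blood is scheduled on cycle 1 day 1. The endpoint as worded therefore does have a baseline in blood.

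Two limits on the evidence also stand. The table may contain merged cells: the single Treatment mark reads as falling under cycle 1 day 15, although dosing is on days 1-7. The PD-marrow mark would still lie in the on-treatment block, and footnote j supports the point without the table. Footnote j and Section 9.3 also refer to a laboratory manual that is not among the documents and might specify a baseline aliquot.

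None of this makes a fresh baseline marrow part of the written schedule.

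**Conclusion.** The point holds in a limited form: a fresh pre-treatment PD marrow is neither scheduled nor assured in AMKL, so paired marrow change from baseline is not guaranteed. The number of patients affected cannot be stated. It depends on how many AMKL patients enrol (24 is only a ceiling, across both diseases) and on whether sites take an unscheduled screening sample.

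The conclusion assumes that the laboratory manual does not already require a screening aliquot, and that the broken table layout hides no PD-marrow mark under Screening. Only exploratory endpoints are touched; the primary safety endpoint and the secondary response endpoint are not. This is a cheap improvement. The Section 9.1 waiver fits the MF schedule, where a marrow from the previous year suffices, and fits badly with the mandatory AMKL screening marrow.

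**What to change.** Make three wording changes, and match them in the laboratory manual.

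- Add a Screening entry to the AMKL row "Bone marrow collection for PD studies".
- State in AMKL footnote j and in Section 9.1: *For AMKL patients whose screening marrow is done after consent, a PD aliquot (10-20 ml, if obtainable) is taken from that aspirate and serves as the marrow baseline for Section 10.1.3. No marrow is repeated for this purpose.*
- Limit the Section 9.1 sentence that waives baseline marrow to MF, or reconcile it with AMKL footnote k.

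The cost is a larger aspirate volume and one more shipment per AMKL patient. The baseline will remain missing where the screening marrow preceded consent, or where the tap was dry. Dry taps are a real possibility, since Section 1.1.1 notes variable marrow fibrosis in AMKL and Appendix I provides for them. The analysis should report how many AMKL patients have a paired marrow.

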6.0 ENDPOINT ASSESSMENT

6.1 Primary Endpoint

The primary objective of this pilot study is to determine the safety profile of alisertib in patients with AMKL and in patients with MF.

Adverse events will be defined according to the National Cancer Institute's Common Terminology Criteria for Adverse Events (NCI CTCAE) version 4.0. The number, frequency, and severity of adverse events will be recorded every cycle for each population. All patients who receive at least 1 dose of alisertib will be considered evaluable for this endpoint.

6.2 Secondary Endpoints

The secondary objective will be to determine preliminary efficacy of alisertib in both populations.

Serial blood and/or bone marrow samples will be collected at specific timepoints for each disease (see Section 5) to determine response to alisertib treatment. Responses will be categorized according to the revised/modified International Working Group (IWG) Response Criteria. Please refer to criteria located in the appendices. Patients who had measurable disease at baseline, receive at least 1 cycle of treatment, and have at least one post-baseline disease assessment will be considered evaluable for this endpoint. Response after cycle 6 (upon completion of C7D1 marrow) will be reported for all evaluable patients.

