Statistical Methodology	All adverse events (AEs) will be summarized using frequencies and percentages. Data on type, timing, frequency and attribution of AEs will be included. To determine preliminary efficacy, response (defined as having at least PR in evaluable patients) will be reported as a proportion and 95% confidence interval using exact binomial methods. Proportions for clinical response (defined as having at least PR or stable disease) will also be calculated. Please refer to Section 10 for more information regarding analysis plan for exploratory objectives. Approximate standard errors for the estimated response rate when the true response rate is 10% are +/- 6% with a sample of 24 patients total, +/- 18% with a sample of 18 patients, +/- 9% with 12 patients and +/- 10% to 12% with 6 patients.
--------------------------------	---

STUDY SCHEMA

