2.2 Secondary Objectives & Endpoints

The secondary objective will be to determine preliminary efficacy of alisertib in both populations.

Serial blood and/or bone marrow samples will be collected at specific timepoints for each disease (see Section 5) to determine response to alisertib treatment. Responses will be categorized according to the revised/modified International Working Group (IWG) Response Criteria. Patients who had measurable disease at baseline, receive at least 1 cycle of treatment, and have at least one post-baseline disease assessment will be considered evaluable for this endpoint. Best response will be reported for all evaluable patients.

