10.1.2 Secondary Endpoint

To determine preliminary efficacy, response (defined as having at least PR in evaluable patients) will be reported as a proportion and 95% confidence interval using exact binomial methods. Given that this is a purely descriptive protocol, there is no set hypothesis regarding the response rate. Proportions for clinical response (defined as having at least PR or stable disease) will also be calculated. Please refer to appendices for detailed explanations of the clinical response criteria for each population.

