10.2 Sample Size and Accrual

MF and AMKL are rare diseases with total prevalence (total number of patients with the disease in the US at any time) under 15,000. NIH considers prevalence under 200,000 a rare disease. A total of 24 subjects (maximum 24 subjects, regardless of the disease breakdown of MF or AMKL. If all 24 were MF, that would be acceptable) will be accrued to this trial. Approximately 4 potentially eligible patients are seen per month at all sites, and it is anticipated that at least 1 per month will be accrued, leading to a 2 year accrual period.

. Approximate standard errors for the estimated response rate when the true response rate is 10% are +/- 6% with a sample of 24 patients total, +/- 18% with a sample of 18 patients, +/- 9% with 12 patients and +/- 10% to 12% with 6 patients. In the event that a patient consents and is registered to the study but never begins treatment, that patient may be replaced. The QAM must be notified and, if necessary, DMC approval must be obtained.

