Appendix I – International Working Group Response Criteria for AML

Definitions of response criteria are based primary on those given by Cheson et al.

Category	Definition
Complete remission (CR) ¹	Bone marrow blasts <5 percent; absence of blasts with Auer rods; absence of extramedullary disease; absolute neutrophil count >1.0 x 10 ⁹ /L (1000/μL); platelet count >100 x 10 ⁹ /L (100,000/μL); independence of red cell transfusions
CR with incomplete recovery (CRi) ²	All CR criteria except for residual neutropenia (<1.0 x 10 ⁹ /L (1000/μL)) or thrombocytopenia (<100 x 10 ⁹ /L (100,000/μL))
Morphologic leukemia-free state ³	Bone marrow blasts <5%; absence of blasts with Auer rods; absence of extramedullary disease; no hematologic recovery required.
Partial remission (PR)	All hematologic criteria of CR; decrease of bone marrow blast percentage to 5 to 25%; and decrease of pretreatment bone marrow blast percentage by at least 50%.
Cytogenic CR (CRc) ⁴	Reversion to a normal karyotype at the time of morphologic CR (or CRi) in cases with an abnormal karyotype at the time of diagnosis; based on the evaluation of 20 metaphase cells from bone marrow.
Molecular CR (CRm) ⁵	No standard definition; depends on molecular target.
Treatment failure	
Resistant disease (RD)	Failure to achieve CR, CRi or PR; only includes patients surviving ≥7 days following completion of initial treatment, with evidence of persistent leukemia by blood and/or bone marrow examination.
Death in aplasia	Deaths occurring ≥ 7 days following completion of initial treatment while cytopenic; with an aplastic or hypoplastic bone marrow obtained within 7 days of death, without evidence of persistent leukemia.
Death from indeterminate cause	Deaths occurring before completion of therapy, or <7 days following its completion; or deaths occurring ≥7 days following completion of initial therapy with no blasts in the blood, but no bone marrow examination available.
Relapse ⁶	Bone marrow blasts ≥ 5%; or reappearance of blasts in the blood; or development of extramedullary disease.

¹ All criteria need to be fulfilled; marrow evaluation should be based on a count of 200 nucleated cells in an aspirate with spicules; if ambiguous, consider repeat exam after 5 to 7 days; flow cytometric evaluation may help to distinguish between persistent leukemia and regenerating normal marrow; a marrow biopsy should be performed in cases of dry tap, or if no spicules are obtained; no minimum duration of response required.

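### Response is planned only in evaluable patients, a set partly fixed after dosing starts; no all-treated rate is planned, and dropping unassessed patients can raise the PR rate but not lower it

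*Combined protocol and SAP*

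**What the plan says.** Section 6.2 limits the response analysis to "Patients who had measurable disease at baseline, receive at least 1 cycle of treatment, and have at least one post-baseline disease assessment". Section 2.2 sets the same three conditions and adds: "Best response will be reported for all evaluable patients". Section 6.2 refers instead to response after cycle 6, but in the same evaluable set. The analysis text in Section 10.1.2 and the Study Summary reads: "response (defined as having at least PR in evaluable patients) will be reported as a proportion and 95% confidence interval using exact binomial methods". A second proportion, PR or stable disease, is also to be calculated, with no separate denominator named.

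A set of all patients with at least one dose does exist, but Sections 2.1, 4.3 and 6.1 use it only for safety and toxicity. Section 10.2 provides for replacement only when a registered patient "never begins treatment, that patient may be replaced". A patient who starts treatment and then proves non-evaluable is therefore not replaced and leaves the response denominator.

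Appendix I lists certain deaths under treatment failure. One group is "Deaths occurring before completion of therapy, or <7 days following its completion"; another is later deaths "with no blasts in the blood, but no bone marrow examination available".

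**The concern.** Receiving one cycle and having a post-baseline assessment are both outcomes of the treatment period. Patients who die, deteriorate or stop early are the ones most likely to miss them. A rate computed after removing such patients describes those who got far enough to be assessed, not everyone who was given the drug. This is the trial's only planned efficacy estimate with a confidence interval, and its purpose is to describe activity in each disease.

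There is also some tension with Appendix I. Section 6.2 says responses follow the appendix criteria, and those criteria count some early or unexamined deaths as failures. The evaluable rule removes the subset of these patients who had less than one cycle or no post-baseline assessment.

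**Working it through.** **The plan's own figure.** Section 10.2 gives a standard error of 6% for 24 patients at a true rate of 10%. √(0.10 × 0.90 / 24) = 0.061, so it reproduces. (The 18% given for 18 patients does not: √(0.10 × 0.90 / 18) = 7.1%. That is a separate matter and is not used here.)

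**Formula.** Let N be patients treated, R responders among them, k patients excluded, and r responders among those excluded. The all-treated rate is R/N and the evaluable rate is (R − r)/(N − k).

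**Direction, by reason for exclusion.**

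1. *No post-baseline assessment.* Such a patient cannot be classed as PR or better, so r = 0 and R/(N − k) ≥ R/N, with equality only if R = 0 or k = 0. The PR rate can rise but not fall.
2. *Assessed, but less than one cycle.* In MF, Appendix II requires benefit to last at least 12 weeks, which is 12/3 = 4 cycles, so a responder here is very unlikely. In AMKL, Appendix I says "no minimum duration of response required" for CR and Section 5.2 schedules an end-of-treatment (EOT) marrow, so an excluded responder is possible. The EOT marrow does not bring that patient back in, because all three conditions must hold.
3. *No measurable disease at baseline.* The direction is unknown.

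**Size.** The documents give no exclusion count, so N, R and k below are assumptions, with r = 0. Intervals are Clopper-Pearson 95%.

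| Treated | Responders | Excluded | All-treated | Evaluable | Shift (points) |
|---|---|---|---|---|---|
| 24 | 2 | 1 | 8.3% (1.0–27.0) | 8.7% (1.1–28.0) | 0.4 |
| 24 | 2 | 2 | 8.3% (1.0–27.0) | 9.1% (1.1–29.2) | 0.8 |
| 24 | 2 | 4 | 8.3% (1.0–27.0) | 10.0% (1.2–31.7) | 1.7 |
| 18 | 2 | 2 | 11.1% (1.4–34.7) | 12.5% (1.6–38.3) | 1.4 |
| 12 | 1 | 1 | 8.3% (0.2–38.5) | 9.1% (0.2–41.3) | 0.8 |
| 6 | 1 | 1 | 16.7% (0.4–64.1) | 20.0% (0.5–71.6) | 3.3 |

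At N = 24 the all-treated interval is 27.0 − 1.0 = 26.0 points wide.

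*Reverse case (possible but unlikely).* Take 3 responders among 24, with 2 excluded for less than one cycle, one of them an AMKL responder. The evaluable rate is (3 − 1)/(24 − 2) = 9.1% (1.1–29.2), against 3/24 = 12.5% (2.7–32.4).

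*PR or stable disease.* Take 10 such patients among 20 assessed, with 4 not assessed. The evaluable proportion is 10/20 = 50.0%. With the 4 kept in the denominator as not assessed it is 10/24 = 41.7%. Had all 4 in truth been stable or better, it would be 14/24 = 58.3%. The evaluable figure is therefore never below the rate that keeps unassessed patients in the denominator, but the true status of those patients is unknown.

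**How many might be excluded.** This depends on which examinations count as a disease assessment, which the plan does not say.

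- Blood counts: from cycle 1 day 4, in which case almost nobody is excluded for lack of an assessment.
- MF palpation and MPN-SAF: from cycle 2 day 1, which is 21 + 1 = day 22.
- Marrow: cycle 2 day 1 (day 22) in AMKL; cycle 7 day 1, which is 6 × 21 + 1 = day 127 (± 14 days), in MF; or EOT in either arm.

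These days assume no treatment delays.

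**The case against.** The evaluable rule is prespecified and has the same three conditions wherever it is defined. The endpoint is secondary, Section 10.1.2 states that there is no hypothesis about the response rate, and no decision depends on it. All of that stands, and it limits the consequence to the reported rate and its interval.

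Four stronger readings are tempting, and the documents do not support them.

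- *That Section 6.2 drops every Appendix I early death.* Treatment continues until progression or unacceptable toxicity, so a death before completion of therapy can come late. An AMKL patient who dies in cycle 3 after the cycle 2 day 1 marrow has received a cycle and been assessed, and stays in if disease was measurable at baseline. The other death category presupposes a blood examination, which might itself count as the assessment.
- *That readers could not see how many patients are missing.* The safety analysis covers every treated patient, so treated and evaluable numbers would normally both be visible. Section 4.8 requires discontinuation reasons on the case report form. What the plan lacks is the all-treated rate and a stated accounting of exclusions, not the underlying data.
- *That one cycle is undefined.* Section 4.2 defines it as 21 days, with days 8 to 21 as rest. Only the handling of missed or held doses is open.
- *That the evaluable rate must be inflated.* That holds only for unassessed patients, and then only if there are some and at least one responder. On a broad reading of disease assessment, which the reference to blood and/or marrow samples favours, there may be very few.

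**Conclusion.** The point holds in a limited form. Response is confined to a set defined partly by events after dosing starts, no all-treated response rate is planned, and treated but non-evaluable patients are not replaced. Omitting patients with no post-baseline assessment can only raise the PR rate or leave it unchanged. For the other two reasons for exclusion the direction is not fixed.

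Under the assumed counts for 24 patients the shift is 0.4 to 1.7 points, against a standard error of 6.1 points and an interval 26.0 points wide. It can be larger in a small disease group: 3.3 points with 6 treated, 1 responder and 1 excluded. The actual number excluded cannot be read from the plan. The change is worth making because it gives a less biased description at almost no cost, not because any trial conclusion is at risk.

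**What to change.** In Sections 2.2, 6.2 and 10.1.2 and the Study Summary:

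- Add the response rate (at least PR) with its exact 95% interval, by disease, among all patients who receive at least one dose. Count patients with no post-baseline assessment as non-responders, and count any assessed response whatever the number of cycles received.
- Keep the evaluable-set rate alongside it, and give the number excluded with the reason for each. Name the examinations that count as a post-baseline disease assessment, so that this number is reproducible.
- Report PR or stable disease on the same all-treated denominator, with not assessed as its own category.

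The cost is protocol and analysis wording: no extra visits, data or patients. The downside is that the reported rate will usually be slightly less favourable.
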